Outcomes to assess the effectiveness of the intervention:

Following the use of POCUS in the general practice consultations the GPs will follow normal procedures for registration of activities in general practice using remuneration codes, fee-specific codes for using POCUS, and referrals in the medical record system. Prior to this study 11 fee-specific codes for 11 different POCUS examinations will be installed in the medical record system. The Primary Sector Data Provider Platform (PLSP) will develop an algorithm that allows for the following data extraction on each participating GP in a given time frame: (1) number of POCUS examinations performed, (2) number of referrals, and (3) number of consultations (outcomes E1-3). PLSP will deliver monthly aggregated data for each participating GP from baseline to 24 months after baseline. These continues data will be summarized to demonstrate variation over time.

For the registration of the clinical effect of POCUS use in the consultation (outcome E4), we will use an adapted version of a questionnaire used in a previous cohort study²⁴. The GPs will be asked to specify the following for each POCUS examination: (1) organs/structures examined with POCUS (drop down menu or free text), (2) whether POCUS use entailed a change in diagnosis (yes/no), (3) whether POCUS use entailed a change in referral (yes/no), (4) whether POCUS use entailed a change in treatment (yes/no), (5) whether POCUS use entailed a change in diagnostic certainty for the GP (yes/no), (6) whether POCUS use was helpful for the GP in terms of making a decision for patient management (5-point Likert scale), (7) whether POCUS use was helpful for the GP in terms of arriving at a diagnosis (5-point Likert scale). GP will assess the questionnaire immediately after performing POCUS during consultations in clinical practice. These categorical data will be collected for each participating GP from day 7 to day 372.

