- (D6) Was the educational intervention too difficult or complex to implement?
- (D7) Did any organisational political, economic or social factors influence the implementation of the educational intervention?
- (D8) Did the setting, including organisational values or norms influence the implementation of the educational intervention?
- (D9) Did you have the capacity (e.g. knowledge and skills) to implement the educational intervention?

And the following questions with a free-text answer category:

- (D10) How must did you have to invest financially to implement the educational intervention?
- (D11) How much time and resources did you have to invest to implement the educational intervention?

Outcomes to assess the feasibility of trial methods

For the assessment of the feasibility of trial methods (outcomes F1-F8), we will evaluate the data quality by calculating the proportion of missing or incomplete registrations, recruited participants in relation to possible number of participants as well as participant retention and adherence. The steering committee will discuss the results and perform a qualitative evaluation based on predefined progression criteria (see section 16c).

Regarding the GP questionnaire (outcome F8), we will pilot test validated scales to determine GPs' perceived stress (Cohen's 10-item Perceived Stress Scale), GPs' job satisfaction (Warr-Cook-Wall Job satisfaction Scale) and GPs burnout symptoms (Maslach Burnout inventory).

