- (D8) Culture: More than 90% of teachers or participants find that the setting, organisational values or norms influenced the implementation of the educational intervention
- (D9) Self-efficacy: Less than 90% of teachers or participants find that they had the capacity (e.g. knowledge and skills) to implement the educational intervention
- (D10) Cost: if costs of implementation the educational intervention exceeds the budget for the research project
- (D11) Resources: if measures of the resources and managing required for the implementation the educational intervention exceeds the budget for the research project

Feasibility of trial methods

- (F1) if we are not able to recruit 66% of the eligible participants
- (F2) if we are not able to retain 66% of participants
- (F3) if we are not able to retain 90% of teachers
- (F4) if less than 90% of teachers delivered the intervention by protocol
- (F5) if less than 90% of participants received the intervention by protocol
- (F6) if less than 90% of data from registers was obtainable and valid
- (F7) if less than 90% of data collection through GP questionnaires was obtainable and valid
- (F8) if less than 90% of data collection through GP questionnaires was obtainable and valid

17 Blinding

[figure not shown]
The researcher cleaning the data set and responsible for analyzing the primary outcome will have no knowledge of participants. He is a researcher with a physiotherapy background.

Data collection, management, and analysis

18a Data collection - Plans for assessment and collection of outcome, baseline, and other trial data

Data will be collected at different timepoints.

Figure 7. Data collection

Register data: Data regarding different POCUS examinations, number of referrals, number of consultations will be delivered by PLSP (outcomes E1-3, I1 and 4). The data are registered prospectively by GPs in the medical records during the consultations from the first teaching seminar (day 7) until 24 months after the first teaching seminar (day 829). We will receive these data retrospectively from PLSP, who will use an algorithm to collect monthly aggregated data for each participating GP.

PLSP will also deliver aggregated data on patients age and gender independent from other study data.

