GP registrations: For the GPs' registration of POCUS effect in the consultation (outcome E4), GPs will use paper registrations in logbooks during the educational intervention (day 7 to 96). Here the registrations are made for the GPs own purpose as part of the learning process. Following the educational intervention, we will ask the GPs to continue making these registrations with the purpose of research, using a QR code to access an online questionnaire. The paper registrations will be collected by the research team at the third teaching seminar (day 97) while the online-questionnaire data are collected continuously from day 97 to 372.

For the reporting of anonymously unwanted cases, GPs will have a QR code and a link for an online questionnaire (outcome E5). These data are collected prospectively continuously during consultations from the day 7 – day 829.

GP questionnaire: For the pilottest of a cross-sectional questionnaire exploring burnout, stress and job satisfaction at 3 months (outcome F8), an online questionnaire will be distributed to participants following the third seminar day and a possible reminder will follow after two weeks. The questionnaire collecting background characteristics on participating GPs will be distributed on the first teaching seminar (day 7).

Online platform: For the evaluation of participant adherence (outcome I2) and reach (outcome I3) we will use the registrations on the online platform (Microsoft Teams) supporting the educational intervention. These are collected retrospectively at the end of the educational intervention (day 97).¹²

Process evaluation questionnaire: For the evaluation of implementation of the educational intervention (outcomes D1-11) a questionnaire will be distributed to teachers and participants following the educational intervention (day 97).

18b Data collection - Plans to promote participant retention and complete follow-up

During the study, the principal investigator is available for consultation for the participating GPs in order to resolve any problems or obstacles. Reminders will be sent to the participating GPs reminding them to scan patients and contact the research team in case of problems.

19 Data management

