We will perform subgroup analysis to explore the effects of participants' background characteristics and type of POCUS examinations performed. This will be elaborated in the SAP.

20c Missing data

Missing values, owing to e.g. premature termination of the questionnaire, are considered completely random and will be declared for each outcome. A sensitivity analysis will be performed in cases, where missing values are not considered random.

Data monitoring

21a Data monitoring committee (DMC).

The principal investigator (CAA) will monitor the data collection and contact the project steering committee in case of problems related to data collection or the validity of the collected data. The principal investigator (CAA) will also contact the steering committee in care of participant drop-out.

21b Description of any interim analyses and stopping guidelines, including who will have access to these interim results and make the final decision to terminate the trial

n/a

22 Harms

The participating GPs will be obliged to report any undesirable effects including Suspected Unexpected Serious Adverse Reactions (SUSARs), Serious Adverse Events (SAEs) and Adverse Events (AEs) related or possibly related to the use of POCUS to the safety committee.

23 Auditing

n/a

Ethics and dissemination

24 Research ethics approval

The study will be performed in accordance with the Declaration of Helsinki. The project was notified to The North Denmark Region Committee on Health Research Ethics.

(Den Videnskabsetiske Komité for Region Nordjylland, reference number 2022-000764) who responded that according to Danish Law (komitélovens § 14, stk. 2), no ethical approval is needed for this project.

As we are collecting patient-related data for the purpose of research, we will seek permission by the health authorities (Application sent October 13th 2022). All patient-related data will be collected retrospectively after this approval is obtained. We will honor our information obligations to patients about the project by making project information available in the GP's clinic as hand-outs and posters.

The project has been registered and conducted according to the regulations of the Danish Data Protection Agency (registration number ID 242-3).

25 Protocol amendments

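### Section 20c presumes completely random missingness, which suits E4 badly: scans with no E4 form fall outside it, and E4 is not set against the register count

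*Protocol*

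**What the plan says.** Protocol section 20c says that missing values, for which it gives a questionnaire broken off early as the example, "are considered completely random and will be declared for each outcome". It then adds: "A sensitivity analysis will be performed in cases, where missing values are not considered random". No trigger or method for that analysis is given.

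Section 12 defines how E4 is collected: "The GPs will be asked to specify the following for each POCUS examination", and then: "These categorical data will be collected for each participating GP from day 7 to day 372". Section 18a splits this window in two. Up to day 96 the GP keeps a paper logbook for his or her own learning. From day 97 the GP is asked to carry on for research purposes, "using a QR code to access an online questionnaire".

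Separately, section 12 has the data platform (PLSP) extract the number of POCUS examinations from 11 POCUS-specific codes in the medical record. The counts come monthly for each GP over 24 months, so they span the whole E4 window.

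On data quality, section 12 says "we will evaluate the data quality by calculating the proportion of missing or incomplete registrations". Section 16c sets the threshold for considering a change: "F7) if less than 90% of data collection through GP questionnaires was obtainable and valid". Neither place names the denominator, and no section says that E4 forms will be compared with the register counts.

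**The concern.** The example in section 20c is a form that was begun and broken off. For E4 the more likely loss is a scan for which no form was opened. The same GP performs the scan, judges its effect and decides whether to register it, so registration may well depend on the result. Completely random missingness is then a poor default.

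Such a scan adds no row to the E4 data set. A list of missing values in started forms will not show it, and the sensitivity analysis has nothing to act on.

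At stake are the E4 proportions for change in diagnosis, referral, treatment and diagnostic certainty, and their course over the year, which section 20a would test by repeated measures ANOVA. E4 is due in the effectiveness article (section 31a), and the study is preparatory to a large stepped-wedge trial (section 6). The 90% criterion F7 is also affected, because its E4 part has no stated denominator.

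**Working it through.** **Inputs.** From the protocol: the E4 unit (one report per scan) and window (day 7 to 372), the monthly register count per GP, and the 90% threshold of F7. Assumed, because the protocol gives no values: the true share p of scans with a change, the ratio k of registration probabilities (scans with a change against scans without), the observed share q, and coverage c other than 90%.

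**1. The plan's own figure.** The protocol states no expected coverage for E4. The nearest figure is the roughly 8400 registrations in section 14. Its stated inputs give 21 GPs × 200 days × 1 scan per day = 4200; reaching 8400 takes 21 × 400. That mismatch is a separate matter, but it means the expected count cannot serve as the E4 denominator.

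**2. What section 20c can act on.** An unanswered item in a started form is a missing value: it can be declared and its pattern examined. A scan with no form is an absent row. Only a count from another source can reveal it, and the register count is the one planned source that does not depend on the E4 form.

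**3. Effect of selective registration.** Observed share = p·k / (p·k + 1 − p).

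| k (assumed) | p = 30% | p = 20% |
|---|---|---|
| 2/3 (reversed) | 0.20/0.90 = 22.2% | 0.133/0.933 = 14.3% |
| 1 (no selection) | 30.0% | 20.0% |
| 1.5 | 0.45/1.15 = 39.1% | 0.30/1.10 = 27.3% |
| 2 | 0.60/1.30 = 46.2% | 0.40/1.20 = 33.3% |
| 3 | 0.90/1.60 = 56.3% | 0.60/1.40 = 42.9% |

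**4. Effect on the trend.** Suppose the true share stays at 30%, with k = 1 in the logbook phase and k = 1.5 after the move to the online form. The observed share then goes from 30.0% to 39.1%, an apparent rise of 9.1 points with no true change.

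**5. Bounds that need no value of k.** With coverage c and observed share q, counting every unregistered scan as no change gives q·c. Counting every one as a change gives q·c + (1 − c). For q = 50%:

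| Coverage c | Lower | Upper |
|---|---|---|
| 90% (F7 threshold) | 0.50 × 0.90 = 45% | 45% + 10% = 55% |
| 70% | 0.50 × 0.70 = 35% | 35% + 30% = 65% |
| 50% | 0.50 × 0.50 = 25% | 25% + 50% = 75% |

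The width is 1 − c, so coverage alone decides how much an E4 percentage can say.

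**The case against.** **Several stronger readings are tempting and are not supported.**

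- A reader might infer that an unregistered scan vanishes altogether and that the bias cannot be detected. It does not vanish: if coded, it is counted in the register for that GP and month, so the shortfall can be seen. What stays unknown is whether the missing scans differ in result.
- A reader might infer that E4 is inflated. Nothing in the protocol shows that scans with a change are registered more often, and the reversed ratio lowers the figure.
- A reader might infer that nothing else measures referral. E2 counts referrals from the register, independently of the E4 form.
- A reader might infer that F7 cannot be calculated. It can, once a denominator is chosen.
- A reader might take the register as the full number of scans. It holds 11 codes while E4 accepts free-text organs, only some GPs are paid for scanning (section 15) so coding may be incomplete, and practice scans on family members are encouraged early on (section 11a) and may carry no code.

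**The other side also has a fair general case.** The sentence in section 20c speaks of missing values and does not expressly call unregistered scans random. A proportion of missing registrations is planned, F7 sets a threshold, and the principal investigator reports data problems to the steering committee (section 21a). The study is a single-group, largely descriptive one, and E4 is openly described as the GPs' reported effect. Missing-data detail often belongs in the SAP.

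**What stands of this.** It limits the size of the point and the claims that can be made. It does not remove the point: section 20b leaves its detail to the SAP, whereas section 20c fixes the default itself, and that default does not fit a per-scan report whose completion is in the hands of the person rating the effect.

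**Conclusion.** The point holds as a moderate one. Section 20c sets a completely random default that suits E4 badly, its provisions do not reach scans with no form, and the protocol does not say that E4 forms will be set against the register count that would show the coverage.

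The bias cannot be sized from the documents. Under the assumed ratios, a true 30% would be observed anywhere from 22% (k = 2/3) to 56% (k = 3). The bounds need no ratio: an observed 50% is compatible with 45% to 55% at the F7 threshold and with 35% to 65% at 70% coverage. They do assume that the register captures all relevant scans and that the answers on completed forms are correct. If coding is incomplete, true coverage is lower and the bounds are too narrow. The protocol supports possible bias in either direction, not demonstrated inflation.

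**What to change.** In section 20c, remove the completely random default for E4 and carry the following into the SAP before it is posted:

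1. **Coverage.** For each GP and month, report E4 registrations divided by the PLSP count of coded POCUS examinations. Limit both to the coded examination types, and base the result mainly on the online phase (day 97 to 372), because earlier logbooks may include uncoded training scans.
2. **Bounds.** Present each yes/no E4 proportion with a lower bound (unregistered scans counted as no change) and an upper bound (counted as change).
3. **Limits.** State that the register is the best available denominator but may be incomplete.
4. **F7.** Use the same denominator for the E4 part of the 90% criterion.

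Two other remedies may suggest themselves but do not solve this problem. Weighting E4 to the register count corrects unequal coverage between GP-months; if k is the same within each of them, every cell keeps the bias in step 3 and so does the weighted result. Restricting to GP-months above some coverage needs an arbitrary cut-off and may select unusually diligent GPs.

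The cost is wording and a merge by GP and month of data already planned. It assumes that each E4 registration can be assigned to a GP and a month. The price in results is wider and less favourable E4 figures.
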